Optimized Health-Related Social Needs Screening and Community Linkages

ID: 2019P000128

2/14/2019

PARTNERS HUMAN RESEARCH COMMITTEE PROTOCOL SUMMARY

Answer all questions accurately and completely in order to provide the PHRC with the relevant information to assess the risk-benefit ratio for the study. Do not leave sections blank.

PRINCIPAL/OVERALL INVESTIGATOR

[name], MPH, Co-Principal Investigator

[name], MPhil, MSHP, Co-Principal Investigator

PROTOCOL TITLE

Optimized Health-Related Social Needs Screening and Community Linkages: Implications for Closing the Gap and Achieving Health Equity

FUNDING

MGH Executive Committee on Community Health (ECOCH) Community Health & Health Equity Grant (primary); MGH Department of Emergency Medicine Faculty Research Fund

VERSION DATE

2/14/2019

SPECIFIC AIMS

Concisely state the objectives of the study and the hypothesis being tested.

Objective: To assess health-related social needs (HRSN) of emergency department (ED) patients and provide linkages to hospital- and community-based services and to understand the most effective method for HRSN screening in the challenging environment of the busy ED.

Hypothesis: Screening for HRSN in the challenging environment of the busy ED can be optimized for increased patient acceptability, improved time efficiency, and minimized disruption to the flow of emergency patient care.

Specific Aims:

Aim 1: To evaluate HRSN screening in the ED using oral and written modalities of the established Partners HealthCare HRSN screening tool.

Aim 2: To use qualitative methods to examine patient satisfaction with the process, explore barriers to screening, and identify salient HRSN missed by the established screener.

BACKGROUND AND SIGNIFICANCE

Provide a brief paragraph summarizing prior experience important for understanding the proposed study and procedures.

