The Partners HealthCare HRSN screening tool is currently in use in the MGH ED to screen Medicare and Medicaid beneficiaries for unmet HRSN related to 9 major categories: transportation, food, housing, ability to pay utility bills, ability to pay for medicines, employment, education, childcare, and elder care. In its current form, HRSN screening is carried out as a one-on-one interview that can last up to an hour, conducted by the ED Medicaid navigator, with patients who present during weekday/daytime hours. Not all patients approached agree to the screening however (33-50% of patients approached for screening decline to participate), and patients have reported unmet needs outside of the 9 major categories screened.

Screening in the ED is exceptionally challenging. Patients may feel too ill to divert their attention from their state of health and must be readily available for the multiple interruptions for reassessments and diagnostic testing. Additionally, private spaces are not always available, and patients may feel embarrassed, or simply too exhausted, to discuss their needs. The most effective screening method for HRSN under these challenging conditions—in other words, the most acceptable to patients, the most efficient in identifying salient, pressing, and actionable barriers to health, and the least disruptive to the flow of emergency care—has not yet been identified. Finally, the impact of HRSN screening is greatest when coupled with streamlined linkages and referrals to community-based social services capable of acting upon the information obtained and assisting individuals to meet their health-related social needs.

The overarching goal of this project is to optimize HRSN screening in the ED. Screening in the health care setting can be achieved via oral (in-person interviews) or written (computer-based surveys) modalities. Using the established Partners HealthCare HRSN screener (permission for use granted), we will examine patients' satisfaction with the screening process

using both modalities. Additionally, we will evaluate HRSN identified and missed by the established screener to understand whether additional or alternative screening questions are relevant and needed for the ED patient population. Finally, we will provide participants with linkages and referrals to community organizations based on their identified unmet HRSN.

RESEARCH DESIGN AND METHODS

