Bilingual research assistants (RA) will screen patients for eligibility based on the predetermined criteria and approach eligible patients with a brief description of the study and opportunity for participation. Interested participants will complete a verbal consent process to reduce the barriers to participation, a brief demographic questionnaire, and an assessment of health literacy (Newest Vital Sign) followed by the Partners Healthcare HRSN screener randomized to an oral v. iPad screening strategy. Randomization will occur after consent. Randomization will be operationalized through use of a randomization list. We will make 500 randomization assignments for an expected study enrollment of 200.

After completion of the screening tool, participants will complete a secondary questionnaire asking about satisfaction with the process, the presence of additional HRSN not recorded by the Partners HealthCare screener, and their perspectives on screening. At the conclusion, all participants will be provided with standardized, bilingual list of community resources to address each of the screening domains. For patients who explicitly request assistance with making these connections, the clinical team will be informed, and a Social Services consult (or ED navigator consult when appropriate) will be recommended.

A subset of enrolled patients will be invited to participate in an in-depth interview. We have chosen to use qualitative interviews to identify the range of opinions regarding screening for HRSN in the ED setting. We will purposively sample to balance recruitment across 4 groups defined by screening strategy (oral v. iPad) and health literacy (high v. limited). The sampling strategy is purposive, designed to make sure the full range of themes is elicited within each prespecified group. Interviews are continued until thematic saturation is reached for each group, the point at which interviews are no longer revealing new information about the primary topic of interest. Although there is no formal sample size for qualitative studies, thematic saturation is generally reached by 12 interviews per group,² and therefore we anticipate completing 48 interviews. As we anticipate fewer Spanish-speaking participants based on ED demographics, all Spanish-speaking patients will be invited to participate in the qualitative interview to ensure a diverse representation of perspectives. These 30-minute qualitative interviews will cover

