Provide a brief description of any foreseeable risks and discomforts to subjects. Include those related to drugs/devices/procedures being studied and/or administered/Performed solely for research purposes. In addition, include psychosocial risks, and risks related to privacy and confidentiality. When applicable, describe risks to a developing fetus or nursing infant.

There are minimal risks to participation in this study. As we will be collecting participant names to avoid duplicate enrollment, there is the potential for loss of confidentiality. All study materials will be kept in a locked cabinet inside a locked office, and the screening log/record of names will be kept separately from the study files, also in a secure location. Audio-recordings of interviews will be transcribed by a HIPAA-compliant vendor who will produce anonymized versions of the files for qualitative analysis.

EXPECTED BENEFITS

Describe both the expected benefits to individual subjects participating in the research and the importance of the knowledge that may reasonably be expected to result from the study. Provide a brief, realistic summary of potential benefits to subjects, for example, "It is hoped that the treatment will result in a partial reduction in tumor size in at least 25% of the enrolled subjects." Indicate how the results of the study will benefit future patients with the disease/condition being studied and/or society, e.g., through increased knowledge of human physiology or behavior, improved safety, or technological advances.

Participants will be provided with a list of hospital- and community-based resources tailored to their specific HRSN as identified via the screening and interview process. We anticipate that this project will assist in the optimization of HRSN screening in the ED by identifying salient HRSN not included in the current Partners HealthCare screener, increasing patient acceptability of screening, improving time efficiency, minimizing disruption to the flow of emergency patient care, and creating a streamlined linkage and referral process with community organizations.

EQUITABLE SELECTION OF SUBJECTS

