The risks and benefits of the research must be fairly distributed among the populations that stand to benefit from it. No group of persons, for example, men, women, pregnant women, children, and minorities, should be categorically excluded from the research without a good scientific or ethical reason to do so. Please provide the basis for concluding that the study population is representative of the population that stands to potentially benefit from this research.

No group of persons will be excluded from the research study based on gender, race, ethnicity, or health insurance status. We will enroll only patients ≥ 18 . For patients under age 18, parents/guardians will be approached for consent and participation.

When people who do not speak English are excluded from participation in the research, provide the scientific rationale for doing so. Individuals who do not speak English should not be denied participation in research simply because it is inconvenient to translate the consent form in different languages and to have an interpreter present.

English- and Spanish-speaking patients will be approached for enrollment in this study.

For guidance, refer to the following Partners policy:

Obtaining and Documenting Informed Consent of Subjects who do not Speak English

https://partnershealthcare-public.sharepoint.com/ClinicalResearch/Non-English_Speaking_Subjects.1.10.pdf

RECRUITMENT PROCEDURES

Explain in detail the specific methodology that will be used to recruit subjects. Specifically address how, when, where and by whom subjects will be identified and approached about participation. Include any specific recruitment methods used to enhance recruitment of women and minorities.

Bilingual RA staff will round in the ED to identify potentially eligible patients. Patients will be approached in the ED by a CITI-certified RA and informed about the opportunity to complete a voluntary and anonymous HRSN screener. If the patient expresses interest in learning more, the trained RA will explain the study to the patient, answer all questions, and obtain verbal consent prior to proceeding with the HRSN screening +/- qualitative interview. A screening log with participants names will be kept to avoid duplicate enrollment.

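### Does it matter that the resource list is standardized in the study procedures but tailored in the benefits text?

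*Protocol*

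**What the plan says.** Linkage to services appears in four places in the protocol.

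- **Specific Aims.** The Objective includes the intention to "provide linkages to hospital- and community-based services".
- **Background and Significance.** The closing paragraph says that "we will provide participants with linkages and referrals to community organizations based on their identified unmet HRSN". The same section counts 9 screened categories and notes that "patients have reported unmet needs outside of the 9 major categories screened".
- **Research Design and Methods, study procedures.** After the screener comes a secondary questionnaire, which covers satisfaction and "the presence of additional HRSN not recorded by the Partners HealthCare screener". Then "all participants will be provided with standardized, bilingual list of community resources to address each of the screening domains". Active help follows a request: "For patients who explicitly request assistance with making these connections", the clinical team is told and a Social Services or ED navigator consult is recommended.
- **Expected Benefits.** Participants are to receive "a list of hospital- and community-based resources tailored to their specific HRSN as identified via the screening and interview process".

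Separately, Recruitment Procedures has patients "informed about the opportunity to complete a voluntary and anonymous HRSN screener", and the same paragraph provides for a log of names to prevent duplicate enrollment. Privacy and Confidentiality keeps that log apart from data files that carry only a study number.

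**The concern.** Read together, the texts seem to describe two procedures. In one, the participant's own needs determine the resources and referrals. In the other, everyone gets the same list and referral waits for a request. They also appear to differ on whether hospital resources are included and on whether needs outside the 9 categories are covered.

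That would matter if staff did not know which procedure to follow, or if a report could not say what participants received. Linkage is in the title and the Objective, and the list is the direct individual benefit put to the ethics committee. The study also asks everyone about needs beyond the screener, so the two descriptions differ most for the participants it particularly wants to hear from. The word anonymous adds a second mismatch, because patients hear it at approach while their names are being logged.

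**Working it through.** The plan has no figure to reproduce here. The check compares the texts and then asks whether any result depends on the difference.

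**1. Standardized or tailored.** The study procedures and Expected Benefits describe the same handout and disagree. Nothing says, for example, that a common list is marked up by need. Expected Benefits also relies partly on the interview, which only a subset completes: 4 groups × 12 interviews = 48, and 48 / 200 = 24%. Tailoring through the interview therefore cannot reach all 200 participants. This conflict stands.

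**2. Hospital or community resources.** The printed list in the procedures names community resources only. The same paragraph adds a Social Services or ED navigator consult, which is hospital-side help. List and consult together satisfy the Objective, so Specific Aims is not in conflict. What remains is a difference in the content of the printed list.

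**3. Trigger for referral.** The Background sentence states a goal. It does not say that referral is automatic or made without a request. A list covering each domain, with a consult for those who ask, can fit it. It is loosely worded, not contradictory.

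**4. Needs outside the 9 categories.** The share of participants with such a need is not given. Assume 5%, 10% or 20%.
- Broad reading, in which the benefits sentence covers needs reported by anyone: 200 × 0.05 = 10; 200 × 0.10 = 20; 200 × 0.20 = 40.
- Narrow reading, in which the sentence means the screener plus the interview: 48 × 0.05 = 2.4; 48 × 0.10 = 4.8; 48 × 0.20 = 9.6.

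The two readings differ by a factor of 200 / 48 = 4.2, and the shares are assumptions. The list itself is not shown. The procedures say what it must address, not that it contains nothing else. No count of affected participants can be drawn from the document.

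**5. Anonymous.** The word is applied to the screener, not to participation. Data files carry a study number, the name log is separate, and no text says whether a key joins them. Foreseeable Risks and Discomforts discloses the collection of names and the resulting risk, and Consent Procedures has confidentiality explained to each participant. The word is loose, but the ethics committee has the facts.

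**6. Effect on results.** The order is approach, consent, randomization, screener, secondary questionnaire, list.
- Satisfaction and screening responses are recorded before the list is handed over.
- The approach wording, including anonymous, precedes randomization and so is common to both groups.
- Neither description of the list varies by group.
- Aim 1 evaluates screening by the two modalities. Aim 2 concerns satisfaction, barriers and missed needs. Neither measures linkage.

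Choosing either description leaves the 100 v. 100 comparison as it is.

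**The case for a change.** The strongest case for acting is that both sentences are current commitments and cannot both be honored. The benefit weighed by the ethics committee is larger than the one the procedures deliver. A participant who reports an unscreened need might reasonably expect something the standardized list may not contain. Rewording would be cheap and would leave randomization, sample size and outcomes alone.

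The textual part of this stands: standardized and tailored conflict, and anonymous is a poor word beside a name log. The consequences are weaker. Staff have a procedures section that says what to hand out and when to involve the clinical team, so it is speculative that they would work from the benefits paragraph instead. A report would describe what was actually given. That rewording leaves design and outcomes alone also shows that nothing statistical would be gained by it.

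**Conclusion.** The inconsistency is genuine but is a slip of wording with no bearing on the analysis. It comes down to one sentence under Expected Benefits against one in the study procedures, plus one adjective in Recruitment Procedures. Specific Aims is not in conflict, and the Background sentence is at most loose. The effect on the oral v. iPad comparison is nil. This rests on two features of the protocol: the list follows the satisfaction questionnaire, and it is the same for both groups.

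The number of participants for whom the two descriptions differ cannot be derived; the ranges above rest on assumed shares. The investigators may wish to align the sentences when the text is next edited, and which description they intend is theirs to say. That is editorial tidying. No change to the design, the outcomes or the analysis follows. The conclusion would differ if receipt of services or success of linkage were made an outcome, which this protocol does not do.
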